3.1.10 The subject is  $\geq 18$  years old.

3.1.11 ECOG performance status  $\leq 1$  (Karnofsky  $\geq 70\%$ , see Appendix A).

3.1.12 Participants must have normal organ and marrow function as defined below:

absolute neutrophil count	$\geq 1,000/\text{mcL}$
platelets	$\geq 100,000/\text{mcL}$
hemoglobin	$\geq 8 \text{ g/dl}$
total bilirubin	$\leq 1.5 \times$ institutional upper limit of normal (ULN) (or $\leq 2.0 \times$ ULN in patients with documented Gilbert's Syndrome)
AST(SGOT)/ALT(SGPT)	$\leq 2.5 \times$ institutional ULN or ( $\leq 3 \times$ institutional ULN for participants with documented liver metastases)
creatinine	$\leq 1.5 \times$ institutional ULN OR creatinine clearance $\geq 40 \text{ mL/min}$ (using Cockcroft-Gault formula) for participants with creatinine levels above institutional ULN.

3.1.13 Female subjects of childbearing potential must have a negative pregnancy test (serum or urine) at screening.

**Note:** Childbearing potential is defined as: participants who have not reached a postmenopausal state ( $\geq 12$  continuous months of amenorrhea with no identified cause other than menopause) and has not undergone surgical sterilization (removal of ovaries and/or uterus).

- 3.1.14 Women participants of childbearing potential must agree to use an adequate method of contraception. For women, contraception is required starting with the first dose of study medication through 150 days (5 months) after the last dose of study medication. Examples of contraceptive methods with a failure rate of < 1% per year include bilateral tubal ligation, male sterilization, established and proper use of hormonal contraceptives that inhibit ovulation, hormone-releasing intrauterine devices, and copper intrauterine devices. The reliability of sexual abstinence should be evaluated in relation to the duration of the clinical trial and the preferred and usual lifestyle of the patient. Periodic abstinence (e.g., calendar, ovulation, symptothermal, or postovulation methods) and withdrawal are not acceptable methods of contraception.
- 3.1.15 Participants on bisphosphonates may continue receiving bisphosphonate therapy during study treatment. Initiation of bisphosphonate or RANKL agent is allowed on study.
- 3.1.16 The participant is capable of understanding and complying with the protocol and has signed the informed consent document.

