### 7.3 Expedited Adverse Event Reporting

In the event of an unanticipated problem or life-threatening complications treating investigators must immediately notify the Overall PI.

Investigators **must** report to the Overall PI any serious adverse event (SAE) that occurs after the initial dose of study treatment, during treatment, or within 100 days of the last dose of Nivolumab and 30 days of the last dose of Ipilimumab. SAEs that occur after 30 days post-treatment must only be reported to the Overall PI if they are determined to be related to Nivolumb or Ipilimumab.

For Multi-Center Trials where a DF/HCC investigator is serving as the Sponsor, each participating institution **must** abide by the reporting requirements set by the DF/HCC. This applies to any medical event equivalent to an unexpected grade 2 or 3 with a possible, probable or definite attribution, unexpected grade 4 toxicities, and grade 5 (death) regardless of study phase or attribution.

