### 7.3.5 Reporting of Pregnancy

If, following initiation of the investigational product, it is subsequently discovered that a study participant is pregnant or may have been pregnant at the time of investigational product exposure, including during at least 5 half-lives after product administration, the investigational product will be permanently discontinued in an appropriate manner (eg, dose tapering if necessary for participant).

The investigator must immediately notify [[contact]](mailto:[contact]) of this event via either the CIOMS, MedWatch or appropriate Pregnancy Surveillance Form in accordance with SAE reporting procedures.

Protocol-required procedures for study discontinuation and follow-up must be performed on the participant.

Follow-up information regarding the course of the pregnancy, including perinatal and neonatal outcome and, where applicable, offspring information must be reported on the CIOMS, MedWatch, BMS Pregnancy Surveillance Form, or approved site SAE form. A BMS Pregnancy Surveillance Form may be provided upon request.

Any pregnancy that occurs in a female partner of a male study participant should be reported to BMS. Information on this pregnancy will be collected on the Pregnancy Surveillance Form. In order for Sponsor or designee to collect any pregnancy surveillance information from the female partner, the female partner must sign an informed consent form for disclosure of this information.

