### 8.1 Nivolumab

#### 8.1.1 Description

Nivolumab is also referred to as BMS-936558-01 or BMS-936558. Nivolumab is a soluble protein consisting of 4 polypeptide chains, which include 2 identical heavy chains and 2 identical light chains. The physical and chemical properties of nivolumab are provided in Table 8.1.1 below. The geometric mean of terminal T-HALF was 25.6 days and the typical clearance was 8.8 mL/h, which are consistent with those of full human immunoglobulin antibodies.

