- b. Medical history includes clinically significant diseases, surgeries, and cancer history (including prior cancer therapies and procedures).
- c. A complete physical examination will be performed at baseline. A limited physical exam will be completed prior to therapy on Days 1,15 and 29 for Cycles 1 and on Day 1 of every cycle beginning with Cycle 2.
- d. All medications taken from the time informed consent is signed through 30 days after the last dose of study therapy will be captured in the participant's electronic medical record.

- e. Vital sign assessments include measurements of heart rate, systolic and diastolic blood pressures, respiratory rate, temperature and weight.
- f. Hematology includes: hemoglobin, hematocrit, platelet count, RBC count, WBC count, and percent and absolute differential count. Results must be available prior to the administration of study drug.
- g. Chemistry testing includes: sodium, potassium, chloride, bicarbonate, glucose, BUN, creatinine, calcium, total bilirubin, total protein, albumin, ALT, AST, and alkaline phosphatase. LDH will be drawn at baseline only (during screening or on C1D1). Results must be available prior to the administration of study drug.
- h. TSH, free T4, ACTH, cortisol, amylase, and lipase will be performed during screening, on Day 1 of Cycles 1-4 and then every other cycle on Day 1. These lab tests should be drawn prior to treatment, however, treatment can be administered prior to the results of these tests.
- i. In female subjects of child-bearing potential as defined in the eligibility criteria, the screening pregnancy test (urine preferred, serum acceptable) must be performed within **7 days** before the first dose of study medication. A urine pregnancy test should be repeated within 24 hours of the first dose of study treatment on C1D1. Urine pregnancy tests should be repeated every 4 weeks (+/- 1 week) while receiving study treatment (this is approximately every other Nivolumab infusion). Any urine pregnancy test that comes back as positive should be confirmed with a serum hCG.

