- p. An optional stool sample may be collected at the time of grade  $\geq 2$  diarrhea after discussion with the PI. As these collections are for exploratory correlative purposes, failure to provide a sample or complete the stool questionnaires at these timepoints will not constitute a protocol violation. See section 9 and/or lab manual for stool collection and processing instructions.
- q. End of treatment visit is to occur within 30 days of final administration of study treatment. End of treatment assessments do not have to be repeated if the same assessments were performed within 7 days (28 days for tumor assessments) prior to the visit.

- r. FACT B and the Rotterdam Symptom Checklist should be completed baseline or C1D1 (any time prior to first dose), D1 of C2-C4, and then on D1 of every other cycle (C6D1, C8D1, etc.) These questionnaires may be found in Appendices C and D.
- s. An adverse event assessment is performed 100 days (-15/+30 days) after the last dose of nivolumab. This may be conducted in person or by phone by the investigator or suitably trained and qualified delegate (i.e. MD, RN, NP, etc).

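### The only scheduled late adverse event contact may fall on day 85, before the 100-day SAE reporting period ends, and required medication capture stops at day 30

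*Combined protocol and SAP*

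**What the plan says.** All days below are counted from the last nivolumab dose unless stated otherwise.

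- **Late safety contact.** Section 10, footnote s: "An adverse event assessment is performed 100 days (-15/+30 days) after the last dose of nivolumab". It may be in person or by phone. The end-of-treatment visit comes earlier, within 30 days of the final dose (footnote q). The adverse event row of the calendar has no mark in the Follow-Up column.
- **SAE reporting.** Section 7.3 requires reporting of SAEs "within 100 days of the last dose of Nivolumab and 30 days of the last dose of Ipilimumab", then narrows it: "SAEs that occur after 30 days post-treatment must only be reported to the Overall PI if they are determined to be related". The footnote to the table in Section 7.3.1 also uses 100 days from the last nivolumab dose.
- **Medications.** Section 10, footnote d, covers medications from consent "through 30 days after the last dose of study therapy will be captured" in the electronic medical record.
- **Pregnancy.** Section 7.3.5 covers exposure "including during at least 5 half-lives after product administration" and gives no number of days. Section 8.1.1 states: "The geometric mean of terminal T-HALF was 25.6 days". Section 2.5.1 gives 24.8 days for nivolumab combined with ipilimumab. Testing is tied to treatment: "Urine pregnancy tests should be repeated every 4 weeks (+/- 1 week) while receiving study treatment" (footnote i). Under Section 3.1.14, "contraception is required starting with the first dose of study medication through 150 days (5 months) after the last dose of study medication".
- **Other follow-up.** Section 5.6 provides annual survival checks through records or provider offices, imaging every 6 to 12 weeks for participants who stopped without progression, and follow-up of adverse events that caused removal from therapy. Missed post-treatment scans are not violations (footnote k).

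**The concern.** A contact can only find events that have already happened. If the one scheduled late assessment may precede the end of the reporting period, a site can follow the calendar exactly and still have no scheduled opportunity to learn of an SAE in the last days of that period.

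The protocol gives reasons to expect late events. Its ipilimumab safety section says that a minority of inflammatory events began weeks to months after the drug was stopped. Safety is the first secondary objective, and Section 13.4 reports toxicity as incidence rates with exact confidence intervals. With 30 patients, one missed event lowers a rate by 1/30, or 3.3 percentage points, and missed ascertainment works only in that direction. Because only related SAEs are reportable after day 30, the events at risk are those attributed to treatment.

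The medication cut-off weakens the record of how late events were treated. The pregnancy rule refers to a period that no required contact is timed to cover.

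**Working it through.** This is day arithmetic; no sample size or power figure is involved.

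**Inputs.** Contact at day 100, -15/+30 (footnote s). SAE period 100 days (7.3). Medication capture 30 days (footnote d). Nivolumab half-life 25.6 days (8.1.1) or 24.8 days (2.5.1). Contraception period 150 days (3.1.14).

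**Step 1: the permitted window.** Earliest 100 - 15 = day 85; latest 100 + 30 = day 130. That is 130 - 85 + 1 = 46 permitted days, of which 15 (days 85 to 99) fall before day 100.

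**Step 2: the pregnancy exposure period.** 5 × 25.6 = 128 days; 5 × 24.8 = 124 days. Both are derived, since Section 7.3.5 gives no number. The documents do not state ipilimumab's half-life. A one-compartment approximation from the clearance and volume in Section 2.3.3 is 0.693 × 5.75 L ÷ 0.0183 L/h ÷ 24 ≈ 9.1 days, so five half-lives are about 45 days and nivolumab sets the longer period.

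**Step 3: shortfall.** This is the end of the period minus the contact day, or zero if the contact comes later.

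| Period | Contact day 85 | Contact day 100 | Contact day 130 |
|---|---|---|---|
| SAE reporting, 100 days | 15 | 0 | 0 |
| Five half-lives, 124 days | 39 | 24 | 0 |
| Five half-lives, 128 days | 43 | 28 | 0 |
| Contraception, 150 days | 65 | 50 | 20 |

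A contact on day 85 leaves days 86 to 100 uncovered; one on day 99 leaves only day 100. Five half-lives are fully covered only by a contact on days 128 to 130 (3 of the 46 permitted days), or on days 124 to 130 (7 of 46) with the shorter half-life.

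**Step 4: medications.** 100 - 30 = 70 days of the SAE reporting period lie beyond required capture. Even treatment for an event that began on therapy can outlast it. Table 6 ends protocol therapy for pneumonitis of grade 3 or higher and has steroids tapered over at least 6 weeks (6 × 7 = 42 days), which is longer than 30 days.

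**Step 5: does other follow-up close the gap?** Annual survival checks are not safety assessments. Post-treatment imaging visits are site contacts, but only for participants without progression, and they may be missed without violation. The adverse event follow-up in Section 5.6 concerns events already known. None is a scheduled adverse event assessment on or after day 100.

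**The case against.** The strongest reply is that the reporting duties do not depend on a call. Investigators must report SAEs through day 100 however they learn of them. Section 7.3.4 is triggered by awareness, and Section 7.3.5 by discovery of a pregnancy. The target is day 100, where the SAE shortfall is zero; the 15-day figure is the early edge of the window. Many participants will also be seen for imaging.

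Much of this stands. It means that late events may be missed, not that they will be, and 15 days is a maximum. It does not explain why the plan's one active check may precede the end of the period it serves.

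Four stronger readings are tempting, and the documents do not support them:

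- A reader might infer that no contact can cover the pregnancy exposure period. The +30 side reaches day 130, beyond both 124 and 128 days. Coverage is possible but not assured.
- A reader might treat day 150 as a reporting deadline needing its own contact. It is a contraception commitment by the participant. The animal findings in Section 2.4.1 concern continued treatment during pregnancy, so they do not by themselves call for new surveillance to day 150.
- A reader might infer that immunosuppressant use will be under-counted in the safety results. Section 13.4 plans no such summary. The end of required capture also does not show that treatment goes undocumented in the medical record.
- A reader might take every event on days 86 to 100 as reportable under the 100-day rule. That rule covers SAEs, and after day 30 only related ones. Section 7.4, on routine reporting of grade 2 or higher events, gives no end date.

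**Conclusion.** The point holds as a gap in assured ascertainment. A compliant late contact can leave up to 15 of the 100 days of the SAE reporting period without a scheduled safety contact after them, and any resulting error lowers the toxicity count. Medications for related events need not be recorded for the last 70 of those days. A contact at the target day ends 24 to 28 days before five half-lives have passed, and one on day 85 ends 39 to 43 days before.

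This assumes that the last nivolumab dose is also the last dose of study therapy, which the two-week nivolumab schedule makes usual, and that no site adds contacts of its own. The documents give no basis for estimating how many events would be missed. The primary endpoint is untouched. The change is worth making because it is specific and nearly free.

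**What to change.** - Change the footnote s window to 100 days (0/+30 days). The latest permitted day stays at 130, and the SAE shortfall becomes zero for every compliant contact.
- Extend footnote d so that medications given for reportable adverse events are recorded through that contact.
- Add a pregnancy question to the same contact for women of childbearing potential. A day-100 call would still end 24 to 28 days before five half-lives; that remainder would rest, as now, on reporting when a pregnancy is discovered.
- Reconcile Sections 3.1.14, 7.3 and 7.3.5 with footnotes d, i and s. State in days what five half-lives means and which half-life is used.

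The cost is an amendment to footnote wording, calls that move later by up to 15 days, and slightly more data entry. These are data-collection changes; no treatment or contraception rule is altered.

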## 11. MEASUREMENT OF EFFECT

For the purposes of this study, participants should be re-evaluated for response approximately every 6 weeks for the first 24 weeks and then every 12 weeks thereafter. If cycles are delayed for any reason, the scan schedule should be moved to align with cycles of treatment received.

### 11.1 Antitumor Effect – Solid tumors

Response and progression in sites of metastases will be evaluated in this study using the international criteria proposed by the RECIST 1.1 criteria [Eisenhauer *et al.*, 2009]. Changes in the largest diameter (unidimensional measurement) of the tumor lesions and the shortest diameter in the case of malignant lymph nodes are used in the RECIST criteria.

#### 11.1.1 RECIST 1.1 Definitions

Evaluable for Target Disease response. Only those participants who have measurable disease outside the field of radiation present at baseline, have received at least one cycle of therapy, and have had their disease re-evaluated will be considered evaluable for target disease response. These participants will have their response classified according to the definitions stated below. (Note: Participants who exhibit objective disease progression prior to the end of cycle 1 will also be considered evaluable.)

Evaluable Non-Target Disease Response. Participants who have lesions present at baseline that are evaluable but do not meet the definitions of measurable disease, have received at least one cycle of therapy, and have had their disease re-evaluated will be considered evaluable for non-target disease. The response assessment is based on the presence, absence, or unequivocal progression of the lesions.

#### 11.1.2 Disease Parameters

Measurable disease. Measurable lesions are defined as those that can be accurately measured in at least one dimension (longest diameter to be recorded) as  $\geq 20$  mm by chest x-ray or  $\geq 10$  mm with CT scan, MRI, or calipers by clinical exam. All tumor measurements must be recorded in millimeters (or decimal fractions of centimeters).

Note: Tumor lesions that are situated in a previously irradiated area are not considered measurable.

Malignant lymph nodes. To be considered pathologically enlarged and measurable, a lymph node must be  $\geq 15$  mm in short axis when assessed by CT scan (CT scan slice thickness recommended to be no greater than 5 mm). At baseline and in follow-up, only the short axis will be measured and followed.

Non-measurable disease. All other lesions (or sites of disease), including small lesions (longest diameter  $< 10$  mm or pathological lymph nodes with  $\geq 10$  to  $< 15$  mm short axis),

are considered non-measurable disease. Bone lesions, leptomeningeal disease, ascites, pleural/pericardial effusions, lymphangitis cutis/pulmonitis, inflammatory breast disease, abdominal masses (not followed by CT or MRI), and cystic lesions are all considered non-measurable.

Note: Cystic lesions that meet the criteria for radiographically defined simple cysts should not be considered as malignant lesions (neither measurable nor non-measurable) since they are, by definition, simple cysts.

‘Cystic lesions’ thought to represent cystic metastases can be considered as measurable lesions, if they meet the definition of measurability described above. However, if non-cystic lesions are present in the same participant, these are preferred for selection as target lesions.

Target lesions. All measurable lesions up to a maximum of 2 lesions per organ and 5 lesions in total, representative of all involved organs, should be identified as **target lesions** and recorded and measured at baseline. Target lesions should be selected on the basis of their size (lesions with the longest diameter), be representative of all involved organs, but in addition should be those that lend themselves to reproducible repeated measurements. It may be the case that, on occasion, the largest lesion does not lend itself to reproducible measurement in which circumstance the next largest lesion which can be measured reproducibly should be selected. A sum of the diameters (longest for non-nodal lesions, short axis for nodal lesions) for all target lesions will be calculated and reported as the baseline sum diameters. If lymph nodes are to be included in the sum, then only the short axis is added into the sum. The baseline sum diameters will be used as reference to further characterize any objective tumor regression in the measurable dimension of the disease.

Non-target lesions. All other lesions (or sites of disease) including any measurable lesions over and above the 5 target lesions should be identified as **non-target lesions** and should also be recorded at baseline. Measurements of these lesions are not required, but the presence, absence, or in rare cases unequivocal progression of each should be noted throughout follow up.

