#### 11.1.3.1 Evaluation of Target Lesions

Complete Response (CR): Disappearance of all target lesions. Any pathological lymph nodes (whether target or non-target) must have reduction in short axis to <10 mm.

Partial Response (PR): At least a 30% decrease in the sum of the diameters of target lesions, taking as reference the baseline sum diameters.

Progressive Disease (PD): At least a 20% increase in the sum of the diameters of target lesions, taking as reference the smallest sum on study (this includes the baseline sum if that is the smallest on study). In addition to the relative increase of 20%, the sum must also demonstrate an absolute increase of at least 5 mm. (Note: the appearance of one or more new lesions is also considered progressions).

Stable Disease (SD): Neither sufficient shrinkage to qualify for PR nor sufficient increase to qualify for PD, taking as reference the smallest sum diameters while on study.

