#### 11.3.1.2 Definition of Target Lesions Response Using irRC

- **irComplete Response (irCR):** Complete disappearance of all target lesions. This category encompasses exactly the same subjects as “CR” by the mWHO criteria.
- **irPartial Response (irPR):** Decrease, relative to baseline, or 50% or greater in the sum of the products of the two largest perpendicular diameters of all target and all new measurable target lesions (i.e., Percentage Change in Tumor Burden). Note: the appearance of new measurable lesions is factored into the overall tumor burden, but does not automatically qualify as progressive disease until the SBD increases by  $\geq 25\%$  when compared to SPD at nadir.
- **irStable Disease (irSD):** Does not meet criteria for irRC or irPR, in the absence of progressive disease.
- **irProgressive Disease (irPD):** At least 25% increase Percentage Change in Tumor Burden (i.e. taking SPD of all target lesions and any new lesions) when compared to SPD at nadir.

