#### 11.3.1.4 Definition of Overall Response Using irRC

Overall response using irRC will be based on these criteria:

- **Immune-Related Complete Response (irCR):** Complete disappearance of all tumor lesions (target and non-target) together with no new measurable/unmeasurable lesions for at least 4 weeks from the date of documentation of complete response.
- **Immune-Related Partial Response (irPR):** The sum of the products of the two largest perpendicular diameters of all target lesions is measured and captured as the SPD baseline. At each subsequent tumor assessment, the SPD of the two largest perpendicular diameters of all target lesions and of new measurable lesions are added together to provide the Immune Response Sum of Product Diameters (irSPD). A decrease, relative to baseline, of the irSPD compared to the previously SPD baseline of 50% or greater is considered an irPR.
- **Immune-Related Stable Disease (irSD):** irSD is defined as the failure to meet criteria for immune complete response or immune partial response, in the absence of progressive disease
- **Immune-Related Progressive Disease (irPD):** It is recommended in difficult cases to confirm PD by serial imaging. Any of the following will constitute PD:
  - At least 25% increase in the SPD of all target lesions over baseline SPD calculated for the target lesions.
  - At least 25% increase in the SPD of all target lesions and new measurable lesions (irSPD) over the baseline SPD calculated for the target lesions.

Criteria for determining overall response by irRC are summarized as follows:

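### Section 11.1.2 restricts lymph-node measurement to the short axis, but the irRC rules in 11.3.1 need two perpendicular diameters of every target lesion; unreconciled, this leaves the secondary irRC endpoints missing or inconsistently derived for nodal disease

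*Combined protocol and SAP*

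**What the plan says.** **RECIST part (11.1).** Section 11.1 describes the unidimensional measurements, noting that "the shortest diameter in the case of malignant lymph nodes are used in the RECIST criteria". Section 11.1.2 sets the entry size for a measurable node at 15 mm in short axis and adds: "At baseline and in follow-up, only the short axis will be measured and followed". For other measurable lesions it asks for the "longest diameter to be recorded". A separate sentence in 11.1.2 governs the RECIST sum: "A sum of the diameters (longest for non-nodal lesions, short axis for nodal lesions) for all target lesions will be calculated". For complete response, 11.1.3.1 says: "Any pathological lymph nodes (whether target or non-target) must have reduction in short axis to <10 mm".

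**irRC part (11.3.1).** Section 11.3.1.4 says: "The sum of the products of the two largest perpendicular diameters of all target lesions is measured and captured as the SPD baseline". The products are then formed again at each later assessment, with new measurable lesions added. A fall of at least 50% is irPR and a rise of at least 25% is irPD. For irCR, 11.3.1.2 requires: "Complete disappearance of all target lesions". The summary table pairs irCR with a change of -100%. None of these rules mentions lymph nodes.

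**Use.** Objectives 1.3.2, 1.3.5 and 1.3.6 are ORR, CBR and PFS by irRC. Several correlative objectives in 1.4 also use irRC response, and section 5.5 refers to irRC progression for patients remaining on therapy.

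**The concern.** The sentence in 11.1.2 concerns what is measured, not only what is summed; the sum has its own sentence. A site cannot obey both 11.1.2 and 11.3.1.4 for a target node. If it obeys 11.1.2, the node has one recorded dimension and no product. The patient's SPD is then either missing or filled by a local convention.

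The study is multicenter, so different sites may choose different conventions. A CT can be re-measured later. Section 11.1.3 also accepts palpable nodes measured with calipers, and there an unrecorded second axis cannot be recovered.

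The missing nodal rule is a second, smaller gap. A node that has shrunk below 10 mm satisfies RECIST CR but has not disappeared, and nothing says how irRC should class it.

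**Working it through.** The plan states no figure on this point, so there is none to reproduce. The check is a comparison of the rules followed by simple arithmetic.

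**Inputs from the documents.** Measurable node: short axis at least 15 mm (11.1.2). RECIST nodal CR: short axis under 10 mm (11.1.3.1). irPR: SPD down 50% or more. irPD: SPD up 25% or more (11.3.1.2, 11.3.1.4). Enrollment: 30.

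**Assumption.** The documents give no node dimensions. All node sizes below are illustrative.

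**Step 1. Which categories depend on the second diameter?**

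| irRC category | Basis | Needs two diameters? |
|---|---|---|
| irCR | disappearance | no |
| irPR | SPD down 50% or more | yes |
| irSD | neither response nor progression | yes |
| irPD | SPD up 25% or more | yes |

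**Step 2. What if only the short axis is recorded?** A site might put the short axis itself against the thresholds, or square it.
- Node from 15 to 9 mm. One axis: 9/15 - 1 = -40%, irSD. Squared: 81/225 - 1 = -64%, irPR.
- Node from 15 to 18 mm. One axis: 18/15 - 1 = +20%, not irPD. Squared: 324/225 - 1 = +44%, irPD.

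The same recorded data give different response and progression calls, so ORR, CBR and PFS by irRC are all exposed.

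**Step 3. Residual node, both diameters recorded.** Write S for the short axis and L for the long axis, with 0 for baseline and 1 for on treatment. For a patient whose only disease is one target node:

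change in SPD = (S1 x L1)/(S0 x L0) - 1

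- 15 x 18 mm to 9.5 x 15 mm: 142.5/270 - 1 = -47.2%. The nodal criterion for RECIST CR is met; irRC gives irSD.
- 15 x 20 mm to 9 x 18 mm: 162/300 - 1 = -46.0%. Same result.
- 15 x 20 mm to 9 x 12 mm (both axes shrink in proportion): 108/300 - 1 = -64.0%, irPR.

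**Step 4. How narrow is the irSD case?** It requires L1/L0 > 0.5 x S0/S1. At S0 = 15 mm:

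| S1 (mm) | L1/L0 must exceed |
|---|---|
| 9.9 | 0.758 |
| 9.5 | 0.789 |
| 9 | 0.833 |
| 8 | 0.938 |

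If the long axis does not grow, S0 must be below 2 x S1, hence 15 to just under 20 mm. Proportional shrinkage always gives irPR, because the fall exceeds 1 - (10/15)^2 = 55.6%. Other disease matters too: adding one 10 x 8 mm non-nodal target that disappears turns the -46.0% case into 162/380 - 1 = -57.4%, irPR.

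**Step 5. Would a zero contribution for nodes under 10 mm be a safe repair?** No. In a node-only patient the nadir SPD would be 0. Section 11.3.1.2 measures irPD from nadir. With a 15 mm long axis, regrowth from 9.5 to 10 mm takes the true product from 142.5 to 150, or +5.3%. Under the zero rule it goes from 0 to 150, which is irPD. RECIST progression on target size needs an absolute increase of at least 5 mm (11.1.3.1); here it is 0.5 mm. Section 11.3.1.4 refers irPD to baseline rather than nadir, so the effect depends on which of the two sections is applied.

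**The case against.** The strongest reply is that 11.1.2 sits inside the RECIST section and 11.3.1 is a separate criterion with its own measurement instruction. On that reading the short-axis sentence governs RECIST only, and 11.3.1.4 already tells sites to capture the products for all target lesions. The CRF is not in the documents and may hold both fields.

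Much of this stands. A reader might infer that irRC endpoints cannot be computed at all for nodal disease. The documents do not support that, because an explicit two-diameter instruction exists. The defect is a contradiction, and data are lost only where 11.1.2 is followed literally.

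Three other readings are also too strong:
- That non-nodal lesions have the same conflict. Recording the longest diameter does not bar recording its perpendicular.
- That irCR depends on two diameters. It rests on disappearance.
- That the different CR rules must be an error. Section 11.3.1.2 ties irCR to CR by the mWHO criteria, not to RECIST CR, so the difference may be intended.

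What the reply does not remove is the word measured in the nodal sentence, the lack of any text limiting it to the RECIST sum, and the silence on residual nodes.

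**Conclusion.** The contradiction is real and should be corrected. If 11.1.2 is followed as written, SPD cannot be formed for target nodes, and irRC ORR, CBR and PFS are missing or inconsistently derived for those patients. The total size cannot be stated, because the documents do not give the share of patients with nodal target lesions. Each patient counts 1/30 = 3.3 points of irRC ORR. The primary RECIST ORR and the two-stage decision are unaffected.

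On the secondary point, a patient with a visible residual node under 10 mm can be a RECIST CR but never an irCR as written. A reader might infer that RECIST complete responders will commonly become irRC non-responders. That is not supported: it needs disease that is nodal or nearly so, a baseline short axis of 15 to under 20 mm (if the long axis does not grow), and little long-axis shrinkage. More often the result is irPR, which still counts in irRC ORR. Even irSD counts toward CBR if it lasts 24 weeks. The examples rest on assumed long axes.

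**What to change.** 1. In 11.1.2, state that the short-axis-only rule applies to the RECIST sum.
2. In 11.1.2 and 11.3.1, require the longest diameter and its perpendicular to be recorded on the CRF for every target lesion, including nodes, and every new measurable lesion, at baseline and each restaging. RECIST sums continue to use short axis for nodes and longest diameter otherwise; irRC uses the product.
3. In 11.3.1, state how a residual node under 10 mm in short axis is classed for irRC response, and reconcile that with the mWHO sentence in 11.3.1.2. Whatever class is chosen, keep the node's measured product in the SPD used as nadir for irPD; do not set it to zero.

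The cost is one extra measurement per lesion at assessments already scheduled, one CRF field if it is not already there, and a wording change. No extra scans are needed.
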